3.5 Prescription and dispensing of treatment. Accounting for study medication

The investigational medication is marketed under the name ROCALTROL 0.25 MCG 20 capsules.

Conservation: at room temperature (20–25°C).

If a patient agrees to participate in the study, the research team will contact the Pharmacy Service to inform of this inclusion.

The Neurology service will prescribe the medication (Calcitriol 0.25 mcg capsules (ROCALTROL®) through a prescription for specially prescribed medications, a model for internal use in the hospital.

Information to be completed by the research team:

- Patient identifying data: patient name and surname, medical record number and assigned patient number
- Prescribing doctor: Name, registered number, signature and date
- Code and/or abbreviated name of the study protocol
- Visit number within the study calendar

The Pharmacy service will dispense to the patient based on said prescription and the period that must be covered until the next study visit (4 months, equivalent to 120-123 days).

The study medication will be properly relabeled in the Pharmacy service as a clinical trial sample. A label will be used for the medication carton with the following information:

Active principle
Pharmaceutical Specialty
Route of administration
Batch and expiration
Name and Number of the patient in the study

and another for the dispensing bag, according to the following model:

STUDY: FA-CALCITRIOL

Promoter: Joint IAS/ICS Neurology Service

Address: [name], [name] Tel. [name]

Researcher: [name] [name]

Patient number

Patient Name.....

_____ packaging ROCALTROL 0.025 mcg 20 Capsules

Store at room temperature.
Protect from sunlight.
KEEP OUT OF THE REACH OF CHILDREN

Sample for clinical research

From the IAS Pharmacy Service, control of the dispensing and return of all dispensed containers will be carried out, counting the medication returned by the patient after

each visit, without prejudice to the fact that said count is also carried out by the research team. , so that there can be a double check on adherence to treatment, by the research team and by the Pharmacy service.

The returned medication will be kept in the Pharmacy service itself, for final counting by the research team. The accounting of medication as well as patient dispensations and returns will be carried out through the Fundanet application.

Expiration control of the study medication will be carried out.

SCHEDULE

| TASKS | MES | | | | | | | | | | | | | | |
|----------------------------|-----|----|---|---|---|---|---|---|---|----|----|----|----|----|----|
| | -2 | -1 | 0 | 1 | 2 | 3 | 4 | 5 | 6 | 7 | 8 | 9 | 1 | 1 | 1 |
| 0 | 1 | 2 | 3 | 4 | 5 | 6 | 7 | 8 | 9 | 10 | 11 | 12 | 13 | 14 | 15 |
| RECLUTAMIENTO | X | X | | | | | | | | | | | | | |
| TREATMENT | | | X | X | X | X | X | X | X | X | X | X | X | X | X |
| FRATAXIN LEVELS | | | X | X | | | | X | | | | X | | | X |
| CALCEMIA MONITORING | | | X | X | | | | X | | | | X | | | X |
| ECG | | | X | X | | | | X | | | | X | | | X |
| NEUROLOGICAL EVALUATION | | | X | | | | | | | | | X | | | X |

4. SELECTION AND WITHDRAWAL OF SUBJECTS

Patient recruitment will be proposed to patients with FA controlled in the Ataxia Unit of the joint Neurology service of the [name] University Hospital and the Santa Caterina Hospital who meet the inclusion criteria and lack exclusion criteria and wish to participate in the study. To reach the desired "n" (20 patients), an invitation to participate will be made through a press release on the websites and publications of

FEDAES (Federation of Ataxias of Spain) and ACAH (Catalan Association of Hereditary Ataxias) (Addendum 2). This invitation will include: the title of the study, description of the objectives, duration of the research, contact email address from which more detailed information will be sent to those interested in participating. The information will be expanded by letter/mail (Addendum 3) to those who request to participate and they will be scheduled for the screening visit.

4.1 Inclusion criteria.

In the screening visit, the inclusion criteria will be assessed:

Patients with FA confirmed by molecular genetic studies, who are between 16 and 65 years old and maintain the ability to walk, even with external support of any type.

4.2 Exclusion criteria.

During the screening visit, a first blood draw will be carried out to assess frataxin levels and a determination of calcium, albumin, glomerular function, vitamin D, sodium, potassium and phosphorus. Patients with hypercalcemia, or impaired glomerular function or elevated creatinine levels will be excluded. A pregnancy test will be carried out in pre-menopausal women.

More specifically, patients affected by some other disease that interferes with the patient's assessment, whether medical or neurological, will be excluded. Patients with severe visual or auditory deficits will also be excluded, as well as those with cognitive impairment (dementia or cerebellar cognitive affective syndrome), or mentally or legally incapacitated subjects. Those affected by serious psychiatric illnesses, or those with a history of substance abuse within the 6 months prior to screening, will also not be admitted. Avoid including patients who have suffered severe allergies to medications, those who present heart disease of a certain entity (detailed in Addendum 4.1 and Addendum 4.2) and those who have taken investigational drugs in the 30 days prior to inclusion. Patients under treatment with digoxin, thiazide diuretics, cholestyramine, corticosteroids, laxatives with magnesium, barbiturates and antiepileptics, calcium or vitamin D will also not be accepted for the study.

Pregnant or breastfeeding women will not be admitted.

Patients who meet the inclusion criteria and those in whom no exclusion criteria are detected will be admitted, then the patient will sign the informed consent.

Instructions will be given for the dosage of treatment with the drug calcitriol (Rocaltrol© 0.25mcgs).

The patient will be provided with the schedule of visits and appointments for the entire study.

4.3. Participation of heterozygotes and healthy subjects

In order to verify the effectiveness of treatment with calcitriol, it is essential to have the levels of frataxin in two situations, firstly, that of healthy controls who do not carry the AF mutation, and secondly, the levels presented by heterozygous individuals. . It is known that the latter have intermediate figures in frataxin levels: higher than those of affected individuals, but lower than those of the population that does not carry the mutation. Heterozygotes are free of FA symptoms and do not present any alterations; in them, although reduced, the amount of protein is sufficient to keep them asymptomatic throughout their lives. It would therefore be a hypothetical ideal level to approach in order to reach a situation close to clinical normality.

Therefore, we will proceed to draw blood to determine levels of frataxin and mitochondrial proteins in these people. Determinations will therefore be carried out either in parents of those affected or in known heterozygous siblings.

The same determinations will be carried out on healthy controls, who, in theory, do not carry the mutation (the conditions of the study do not allow us to verify the presence of the mutation in this group). The prevalence of the FA mutation in the general population is 1/100).

In these determinations, the levels of frataxin and mitochondrial proteins will be assessed. The data obtained will allow a comparative study between the values of healthy individuals, heterozygotes, and those affected by FA, and in these their basal levels and those obtained during treatment with calcitriol.

Therefore, the following will be chosen for each patient included in the study:

- A healthy control heterozygous for FA, choosing the volunteer parent who attends the screening visit or, if possible, a heterozygous sibling. It will be verified that the heterozygous healthy control does not have any neurological disease, nor any disease related to the metabolism of calcium or Vitamin D and that it is not being treated with Calcium or Vitamin D.

- A non-familial healthy control and therefore supposedly not heterozygous for FA (n=20). You must not have any neurological disease, any disease related to calcium or vitamin D metabolism and you must not be under treatment with calcium or vitamin D.

Once the healthy controls have been chosen, blood will be drawn, after signing the specific informed consent for this type of collaboration.

4.4. Subject withdrawal criteria.

Will be removed from the study:

- to. Any patient who presents hypercalcemia during the controls carried out throughout the trial.
- b. Subjects who present with ECG abnormalities indicative of possible hypercalcemia or arrhythmias during treatment with calcitriol.
- c. Those who repeatedly skip taking treatment.
- d. Those affected who present a new disease or require supplementary treatment that may make the interpretation of the results difficult.

Patients with hypercalcemia and those with ECG abnormalities will continue to be monitored until resolution of symptoms or recorded abnormalities (see Addendum 6).

Telephone or email contact will also be maintained with the patients in section d), although they will not re-enter the study.

Controls with those in section c) will not be followed.

A notification of a serious adverse effect will be made if this occurs (see Addendum 7).

The date of withdrawal from the study and the reason for this, as well as the evolution followed by the patient, will be noted in the CRD.

Subjects who drop out of the study will not be replaced by others as long as the "n" of the study remains between 15 and 20.

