There is currently no effective treatment to correct frataxin deficiency in PA, so a drug that has the ability to increase frataxin production to levels at least similar to those of heterozygotes (healthy carriers) could correct or reduce neurological and cardiological deficits in this disease. (Britti et al., Calcitriol increases frataxin levels and restores altered markers in cell models of Friedreich Ataxia. Under revision in "Cell Death & Disease").

Several investigations have at some point obtained an increase in the production of frataxin with other drugs (eg: EPO, nicotinamide, interferon gamma, resveratrol or rosuvastatin). These products achieved smaller increases in frataxin production in the laboratory than those achieved with calcitriol. Although most of them have been followed by the corresponding trials, none of them have provided results that show a significant effect on the clinical situation of patients. Others are ongoing as a study with etravirine (a drug that increases frataxin production by 50%), or are repeated with modifications due to adverse effects or ineffectiveness (nicotinamide, resveratrol).

1.3 Summary of known and potential risks and benefits.

Calcitriol is a drug on which there is vast experience, it has been used for decades in all diseases related to inability of renal synthesis of calcitriol. It has few contraindications: hypersensitivity to the active substance or to any of the excipients included. It should not be administered to patients with hypercalcemia or evidence of vitamin D toxicity. The potential adverse effects are well known (see Addendum 6). Since the most common adverse reaction is hypercalcaemia, successive monitoring of calcium levels will be performed throughout the study and patients will be monitored for symptoms related to hypercalcaemia.

1.4 Description and justification of route of administration, dose, dosage schedule and treatment period.

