5. SUBJECTS TREATMENT

5.1 Trial treatment.

The only treatment in the study is calcitriol (Rocaltrol©) at 0.25 micrograms/day orally.

5.2 Allowed medications.

Patients under treatment with idebenone or coenzyme Q10 for years.

De novo inclusion of idebenone will only be permitted in patients who develop signs of cardiomyopathy during the study.

5.3 Not allowed medications.

They will not be able to enter the study, but patients who require treatment with digoxin, amiodarone or thiazide diuretics, corticosteroids, cholestyramine, magnesium laxatives, barbiturates and antiepileptics, calcium or vitamin D will not be included or withdrawn.

Nor those who continue treatment with other tested drugs other than idebenone, which include: diperiprone, EPO, resveratrol, nicotinamide, etravirine, rosuvastatin, interferon of any type, EPI743 (vatiquinone), CTI-1601, RT001 (stabilized linoleic acid), pioglitazone, lericlitazone (MIN-102), epicatechin, ovameloxolone, VP 20629 (propionic acid), varenicline, ginko biloba, alpha-tocopherol-quinone.

If a patient has followed a treatment in a clinical trial with any of these drugs, they will be allowed to enter the study only after a washout period of 6 months.

Other drugs will be admitted as long as these drugs do not interfere with the assessment of the results or the neurological function of the patients or modify the calcium levels directly or indirectly.

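### Section 4.3 limits control medication only for calcium and vitamin D, so controls taking drugs the protocol itself describes as frataxin-raising can enter the reference groups

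*Combined protocol and SAP*

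**What the plan says.** Section 4.3 plans one heterozygous control and one unrelated control for each patient. The heterozygous control is found by "choosing the volunteer parent who attends the screening visit or, if possible, a heterozygous sibling". The unrelated control is described as "A non-familial healthy control and therefore supposedly not heterozygous for FA (n=20"). Both groups must be free of neurological disease. The other conditions for the heterozygotes are "nor any disease related to the metabolism of calcium or Vitamin D and that it is not being treated with Calcium or Vitamin D", and for the unrelated controls that they not have "any disease related to calcium or vitamin D metabolism and you must not be under treatment with calcium or vitamin D". No other medicine is mentioned for either group.

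Section 1.2 reports that research groups have at some point obtained an "increase in the production of frataxin with other drugs (eg: EPO, nicotinamide, interferon gamma, resveratrol or rosuvastatin"). It describes etravirine as "a drug that increases frataxin production by 50" percent. On size it says: "These products achieved smaller increases in frataxin production in the laboratory than those achieved with calcitriol".

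Section 5.3 lists medicines not allowed in patients, including "diperiprone, EPO, resveratrol, nicotinamide, etravirine, rosuvastatin, interferon of any type". Its wording concerns patients. Its 6-month washout applies to a patient who took a listed drug in a clinical trial.

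Section 4.3 treats the control levels as indispensable for judging whether calcitriol works, and the heterozygote level as the one treated patients would ideally move towards. Section 9.2 compares baseline frataxin in healthy controls and patients by a t test or Mann-Whitney test, with no adjustment for medication stated.

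**The concern.** The protocol already accepts that a control's medicines can matter, since it bars calcium and vitamin D. It does not extend this to the drugs it names as moving the measured protein. Patients and controls are measured for the same protein in platelets, but only patients are kept off those drugs.

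If some controls take such a drug and it acts in their platelets, the reference mean is too high. The baseline gap between patients and controls then looks wider than it is, and patients on calcitriol look further from the heterozygote level than they are. If nobody asks about medication at the draw, the effect cannot be examined later without going back to the controls.

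**Working it through.** **1. The rules side by side.**

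| Item | Patients (5.3) | Heterozygous controls (4.3) | Unrelated controls (4.3) |
|---|---|---|---|
| Calcium, vitamin D | barred | barred | barred |
| EPO, nicotinamide, resveratrol, rosuvastatin, etravirine | barred | not mentioned | not mentioned |
| Interferon gamma | barred (interferon of any type) | not mentioned | not mentioned |
| Washout | 6 months, after clinical-trial use | none | none |

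All six drugs that section 1.2 names as raising frataxin are on the patient list. None is on either control list.

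**2. How often a control is sampled.** Section 11.2 budgets 140 frataxin determinations. Section 3.4 gives five patient samples: baseline, 15 days, and 4, 8 and 12 months. Then 20 patients × 5 = 100, and 20 heterozygotes + 20 unrelated controls = 40 single samples; 100 + 40 = 140. The budget therefore fits one sample per control, which makes that draw the natural time to ask about medication.

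**3. Illustrative shift in a control mean.** The plan states no figure for this, so there is nothing to reproduce. The group size of 20 comes from section 4.3. The number of users k (1 to 4) and the rise per user e (20% to 50%) are assumptions. The upper value of e borrows the etravirine figure from section 1.2, which is not known to apply to the other drugs or to control platelets.

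Shift in mean = (k/20) × e

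| Users among 20 | e = 20% | e = 50% |
|---|---|---|
| 1 | 1% | 2.5% |
| 2 | 2% | 5% |
| 3 | 3% | 7.5% |
| 4 | 4% | 10% |

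**4. Effect on a comparison with the reference.** If the reference is too high by a fraction s, a patient group truly at 100% of the heterozygote level reads as 100/(1 + s). With s = 1% this is 100/1.01 = 99.0%; with s = 10% it is 100/1.10 = 90.9%.

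**5. Chance of at least one user among 20.** This is 1 − (1 − p)^20 for an assumed usage rate p: 33% at p = 2%, 64% at 5%, 88% at 10% and 99% at 20%. The documents give no usage rate, so these figures only show that one or more users is not a remote event.

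**The case against.** The strongest objection is that no effect in the relevant people is documented. Section 1.2 speaks of increases in the laboratory and gives no figure for rosuvastatin, nicotinamide or resveratrol. Nothing shows that any of these drugs raises platelet frataxin in a heterozygote or a non-carrier. The shift is also not set against between-person spread or assay variation, because the documents give neither. And if all controls already lie above all patients, a rank test would not change at all. This stands: the gap in the rule is certain, the bias is only possible.

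Section 5.3 also gives no assay-related reason for its list. It is a list of drugs tested in the disease and includes several that section 1.2 does not call frataxin-raising. The mismatch shown above therefore rests on reading 1.2 and 5.3 together, and not on a rationale the protocol states.

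Several stronger readings are tempting and are not supported:

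- A reader might infer that a site must accept any control who passes the listed checks. Section 4.3 says controls are chosen and must be healthy. It does not say that everyone who passes must be taken. It simply offers no stated ground for refusal on these drugs.
- A reader might infer that controls are checked for nothing but calcium and vitamin D. Neurological disease and calcium or vitamin D metabolic disease are also checked; the gap concerns medication.
- A reader might infer a large bias because parents are older and often take statins. The documents name only rosuvastatin, give no usage rate, and allow a sibling in place of a parent.
- A reader might infer that efficacy conclusions are at risk. The primary variables in section 3.1 are neurological tests, and section 6.1 defines the frataxin outcome against the patient's own baseline. Section 9.2 sets no response threshold based on heterozygotes. An inflated reference would make calcitriol look less close to target, not more.

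Finally, the case record form and the control consent forms (Addenda 10.3 and 10.4) were not available to check, so a medication question there cannot be excluded.

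**Conclusion.** The point holds in a limited form. As written, section 4.3 lets in controls who currently take drugs that section 1.2 says raise frataxin, while section 5.3 keeps patients off them. What could be distorted is the baseline comparison of patients with controls in section 9.2, and the descriptive use of the heterozygote and healthy levels in section 4.3.

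The size is unknown. The 1% to 10% range rests wholly on the assumed 1 to 4 users and 20% to 50% rise, and on the drugs acting in control platelets at all. The primary neurological endpoint and the within-patient frataxin change do not depend on the controls. The severity is minor. It is worth correcting because the reference levels are given a clear role and the correction costs little.

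**What to change.** In section 4.3, add to the restrictions for both control groups current use of the drugs that section 1.2 names as raising frataxin: EPO, nicotinamide, interferon gamma, resveratrol, rosuvastatin and etravirine. Do not cite the 6-month period in section 5.3 as an existing general washout, since it covers only earlier clinical-trial use.

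Ask about and record each control's medication at the blood draw. Where the attending parent takes one of these drugs, use the other parent or a known heterozygous sibling if possible; section 4.3 already allows for parents or siblings. Where no substitute exists, keep the record and state in section 9.2 that the frataxin comparison will be repeated without that control.

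The cost is one sentence in 4.3, one in 9.2 and one question at the draw. The downside is that a few controls may be swapped or left out, which slightly reduces the control count.

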5. SUBJECTS TREATMENT

5.1 Trial treatment.

The only treatment in the study is calcitriol (Rocaltrol©) at 0.25 micrograms/day orally.

5.2 Allowed medications.

Patients under treatment with idebenone or coenzyme Q10 for years.

De novo inclusion of idebenone will only be permitted in patients who develop signs of cardiomyopathy during the study.

5.3 Not allowed medications.

They will not be able to enter the study, but patients who require treatment with digoxin, amiodarone or thiazide diuretics, corticosteroids, cholestyramine, magnesium laxatives, barbiturates and antiepileptics, calcium or vitamin D will not be included or withdrawn.

Nor those who continue treatment with other tested drugs other than idebenone, which include: diperiprone, EPO, resveratrol, nicotinamide, etravirine, rosuvastatin, interferon of any type, EPI743 (vatiquinone), CTI-1601, RT001 (stabilized linoleic acid), pioglitazone, lericlitazone (MIN-102), epicatechin, ovameloxolone, VP 20629 (propionic acid), varenicline, ginko biloba, alpha-tocopherol-quinone.

If a patient has followed a treatment in a clinical trial with any of these drugs, they will be allowed to enter the study only after a washout period of 6 months.

Other drugs will be admitted as long as these drugs do not interfere with the assessment of the results or the neurological function of the patients or modify the calcium levels directly or indirectly.

5.4 Hypercalcemia treatment

The risk of hypercalcemia with Calcitriol 0.25mcg/24h is very low. It increases in patients in situations of prolonged immobilization, treatment with digoxin and thiazide diuretics among others, these patients being already excluded from the study.

The treatment of hypercalcemia will be based on the severity of the hypercalcemia (see Addendum 8):

- Mild hypercalcemia (Calcium 10.2-12mg/dl): withdrawal of treatment, abundant water intake and analytical control after 7 days.
- Asymptomatic moderate hypercalcemia (Calcium 12-14mg/dl): similar to the treatment of mild hypercalcemia, possibility of treatment with Prednisone 20-40mg/24h
- Moderate symptomatic hypercalcemia (Calcium 12-14mg/dl): withdrawal of treatment. Hospital admission for hydration with physiological saline, treatment with Pamidronate (a bisphosphonate), analytical control at 12-24 hours.

- Severe symptomatic hypercalcemia (Calcium >14mg/dl): withdrawal of treatment. Hospital admission for hydration with physiological saline, treatment with Zolendronate (a bisphosphonate), evaluate treatment with subcutaneous Calcitonin and Prednisone, analytical control at 12-24 hours.

5. 5 Procedures to monitor subject compliance. Patient's diary.

At each visit the patient will be given a "Patient's Diary" in which they will be asked to write down the date, check a box if they take the treatment, and write a note if any new symptoms appear or any abnormality occurs related to taking the treatment. The patient will provide this list at each visit (see Addendum 9).

